# 12.4 Recording of AEs and SAEs

All AEs, regardless of seriousness, severity, or presumed relationship to study treatment, must be recorded using medical terminology in the eCRF and/or other sources. Whenever possible, diagnoses should be given when signs and symptoms are due to a common aetiology (e.g., cough, runny nose, sneezing, sore throat, and head congestion may be reported as "upper respiratory infection"). Investigators must record in the eCRF the date of onset of the event, their opinion concerning the relationship of the event to the study treatment, severity of the event, whether the event is serious or nonserious, actions taken to manage the event, the outcome of the event, and date of resolution where applicable.

Any change to the severity of an AE must be recorded as a comment in the eCRF.

# 12.5 Reporting of SAEs and SUSARs

The Investigator must notify the study Sponsor Safety Department and Sponsor designated safety officer within 24 hours of becoming aware of the occurrence of an SAE. Information regarding SAEs will be transmitted to the Sponsor Safety Department using an SAE form as described in the study SAE Report Form Completion Guidelines.

The SAE form must be completed and signed by a member of the investigational staff and transmitted to the Sponsor Safety Department and Sponsor designated safety officer (Table 8). Any new or updated clinical information on the SAE will be recorded on a new SAE form and sent to the Sponsor Safety Department within 24 hours of the information being available. The initial and follow-up reports of an SAE should be transmitted by email. Receipt of the SAE form must be confirmed by each recipient.

## 12.6 Follow-up of AEs and SAEs

Following initial observation of an AE/SAE, the Investigator is required to proactively follow progress of the relevant participant. Any information obtained in relation to the status of the AE/SAE and the condition of the participant must be appropriately documented in the eCRF or in a follow-up SAE form.

All AEs and SAEs documented at a previous visit/contact and are designated as ongoing, will be reviewed at subsequent visits/contacts. Adverse events/SAEs that have not resolved by the end of the study, or that have not resolved upon discontinuation of the participant's involvement in the study, must be followed until any of the following occurs:

- The event resolves
- The event stabilises
- The event returns to baseline if a baseline value is available
- The event can be attributed to agents other than the study treatment or to factors unrelated to study conduct
- It becomes unlikely that any additional information can be obtained (participant or health care practitioner refusal to provide additional information, lost to follow-up after demonstration of due diligence with follow-up efforts)

The Investigator will ensure that AE/SAE follow-up includes any supplemental investigations as may be indicated to elucidate the nature and/or causality of the event. This may include additional laboratory tests or investigations, histopathological examinations, or consultation with other health care professionals.

The Sponsor may request that the Investigator perform or arrange for the conduct of supplemental measurements and/or evaluations to elucidate as fully as possible the nature and/or causality of the SAE. If a participant dies during participation in the study or during a recognised follow-up period, the Sponsor will be provided with a copy of any post-mortem findings, including histopathology.

New or updated information will be recorded on a new SAE form and sent to the Sponsor.

Due to the coronavirus SARS-COV-2 (COVID-19) pandemic, Investigators must also ensure compliance with local governing legislation and reporting requirements associated with COVID-19 infections.

# 12.7 Exposure In Utero Management and Reporting

In instances of pregnancies or suspected pregnancies identified or reported for any female participant (or male participant's female partner), including a positive pregnancy test regardless of age, during participation in this study, the pregnant female participant (or the male participant's female partner) will be advised to notify her healthcare provider.

The Investigator will notify the Sponsor and designated study safety officer of this event and document the pregnancy on the EIU form as described in the study Pregnancy/EIU Report Form Completion Guidelines.

The Investigator shall obtain informed consent from the pregnant female participant (or male participant's female partner) in order to allow him/her to review relevant medical records and conduct follow-up throughout the gestational period and on the infant following delivery. The Investigator shall follow-up newborn infants that have been exposed to study treatment *in utero* for a minimum of 12 months. Upon discovery of any congenital anomalies (or neonatal deaths) the Investigator shall submit a follow-up report to the Sponsor (and study safety officer) using an SAE Form (as per study Safety Reporting Plan) including information regarding the status of the newborn. A miscarriage or abortion shall also be reported by the Investigator to the study Safety Officer (and the Sponsor) using an SAE Form.

## 12.8 Safety Review Committee

The decision to enrol Group 2 will be made following the evaluation of all available safety data by the SRC up to and including Day 8 of Group 1 (details described in the study SRC Charter). There are no other formal requirements for an SRC meeting, however safety and tolerability data will be continually reviewed and an ad-hoc SRC meeting may be called at any time, if requested by the Investigator (in consultation with the study Sponsor).

At a minimum, the SRC will consist of the Investigator(s) who have enrolled patients in the current group, an IMM and the SMR, however all Investigators involved in the study will be invited to attend each SRC review meeting, regardless of whether they have enrolled participants into the group. Other individuals (e.g., medical experts) may be invited to participate at the discretion of the SRC to provide additional input into the review process if required.

All decisions will be made by agreement between the Investigator(s) and the SMR.

## 13 STATISTICS AND DATA ANALYSIS

Detailed methodology for summaries and statistical analyses of the data collected will be documented in a separate Statistical Analysis Plan (SAP) and will be finalised before database lock. Any changes to the methods described in the final SAP will be described and justified as needed in the clinical study report (CSR).

This section describes the general framework to be used for the analysis and presentation of data in this study. The information described in this section may be revised during the study to accommodate protocol amendments and to make changes to adapt to unexpected issues in study execution and data that could affect planned analyses. All available data will be included in data listings. Data tabulations will be performed for specific analysis populations.

## **13.1** Sample Size Considerations

Up to a total number of 141 healthy subjects (male and female) are planned to be enrolled in

mAbxience Research SL

the study. Subjects who meet the entry criteria will be randomised to receive a single dose of MB05, EU-sourced Synagis® or US-sourced Synagis® in a 1:1:1 fashion. Randomisation will be stratified based on the subject's body weight (50 to <75 kg and  $\geq$ 75 to 95 kg) and gender (male and female). To achieve balance, the number of subjects enrolled in each stratum should be a multiple of 3, where possible.

The reported coefficients of variation (CVs) for AUC and  $C_{max}$  for Synagis® vary between 0.25 and 0.35. Based on a worst-case CV of 0.35 (Robbie et al., 2012), alpha of 0.05 (i.e., utilising a two-sided 90% CI around the mean difference) and a true hypothesised ratio for the mean difference of 0.95, a total of 141 subjects (47 subjects per arm respectively), 1:1:1 ratio) will provide approximately 85% power to demonstrate bioequivalence of MB05 with EU-sourced Synagis® and US-sourced Synagis®. Assuming a 5% dropout, a total of 132 evaluable subjects (44 subjects per arm) are sufficient for this measure.

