# 13.6.2 Serum Pharmacokinetic Parameters and Bioequivalence Analysis

Serum palivizumab concentrations from samples collected at specific timepoints following IM administration of each study treatment will be used to calculate PK parameters using non-

compartmental analysis methods. The following PK parameters will be determined:

- Cmax Maximum observed serum concentration obtained directly from the concentration versus time data.
- Tmax Time to maximum observed concentration, taken directly from the data. If the maximum serum concentration occurs at more than one time point, the first is chosen.
- kel Terminal elimination rate constant obtained from the slope of the line, fitted by linear least squares regression through the terminal points of the logarithmic concentration-time profiles.
- AUCt Area under the serum concentration-time curve from time zero to time t
- $t_{\frac{1}{2}}$  Apparent terminal half-life, calculated as  $t_{\frac{1}{2}} = \ln (2)/k_{el}$ .
- CL/F Apparent total serum clearance of drug after IM administration, where F is the fraction of drug absorbed, calculated as (Dose / AUC0-inf).
- $\label{eq:Vz/F} Vz/F \qquad \mbox{Apparent volume of distribution during terminal phase after IM} \\ administration, calculated as (CL/F / k_{el}).$

PK parameters for each participant will be listed and summarised by treatment using descriptive statistics.

Bioequivalence between MB05 and EU-Synagis®, between MB05 and US-Synagis® and between EU-Synagis® and US-Synagis® will be investigated for AUC0-inf and Cmax by analysis of variance using log-transformed PK parameter values. Bioequivalence will be assessed by calculating the 90% CIs for the ratio of the least squares geometric means for each pairwise comparison and each PK parameter. Bioequivalence will be concluded where the 90% CIs for the ratio of least squares geometric means are contained within the range 80.00% to 125.00%. For each pairwise treatment comparison and each PK parameter, this corresponds to undertaking two one-sided tests (TOST) of significance each at the 5% level.

Additional details of PK analysis will be provided in the study SAP.

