## **3** SAMPLE SIZE

Up to a total number of 141 healthy subjects (male and female) are planned to be enrolled in the study. Subjects who meet the entry criteria will be randomised to receive a single dose of MB05, EU-sourced Synagis® or US-sourced Synagis® in a 1:1:1 fashion.

The reported coefficients of variation (CVs) for AUC and Cmax for Synagis® vary between 0.25 and 0.35. Based on a worst-case CV of 0.35 (Robbie et al., 2012), alpha of 0.05 (i.e., utilising a two-sided 90% CI around the mean difference) and a true hypothesised ratio for the mean difference of 1, a total of 135 subjects (45 subjects per arm respectively), 1:1:1 ratio) will provide approximately 85% power to demonstrate bioequivalence of MB05 with EU-sourced Synagis® and US-sourced Synagis®. Assuming a 5% dropout, a total of 141 subjects (47 subjects per arm) are sufficient for this measure.

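### The protocol's 85% power does not follow from its own inputs: it is about 77% with 47 per arm and 74% with 44, and the SAP reaches 85% only by moving the true ratio from 0.95 to 1

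*Protocol*

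**What the plan says.** Protocol section 13.1 reports that published CVs for AUC and Cmax "vary between 0.25 and 0.35". It then plans as follows: "Based on a worst-case CV of 0.35", "alpha of 0.05 (i.e., utilising a two-sided 90% CI around the mean difference"), and a "true hypothesised ratio for the mean difference of 0.95". From these it concludes that "a total of 141 subjects (47 subjects per arm respectively), 1:1:1 ratio) will provide approximately 85% power to demonstrate bioequivalence" of MB05 with each reference product. On losses it adds: "Assuming a 5% dropout, a total of 132 evaluable subjects (44 subjects per arm) are sufficient for this measure".

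Protocol section 13.6.2 fixes the rest of the test. Parameters are log-transformed, the 90% confidence interval must lie within 80.00% to 125.00%, and this amounts to "undertaking two one-sided tests (TOST) of significance each at the 5% level".

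SAP section 3 keeps the CV, the alpha and the 85%, but attaches them to "a true hypothesised ratio for the mean difference of 1, a total of 135 subjects (45 subjects per arm respectively"). Here 141 is the number enrolled after allowing for dropout, not the number that gives the power.

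SAP section 1 says that differences from the protocol's statistical considerations will be set out in section 18. Section 18 lists none, and the SAP's summary of changes does not mention sample size.

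**The concern.** The same 85% is tied to two different true ratios and two different sample sizes, in documents that are both current: the SAP names protocol version 2.0 as its basis. In a bioequivalence test, power falls quickly as the true ratio moves away from 1. A ratio of 0.95 with 47 per arm and a ratio of 1 with 45 per arm therefore cannot both give about 85% at the same CV.

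The protocol also places the 85% at 141 subjects and then calls 132 sufficient, so it is unclear which number carries the claim.

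At stake is the stated chance that the trial meets its primary objective. An ethics committee or regulator who reads 85% would be relying on a property that the design lacks under the protocol's own planning ratio.

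**Working it through.** **Inputs.** CV 0.35, 5% per one-sided test, true ratio 0.95, and 47 or 44 per arm (protocol 13.1). Log scale and limits 0.80 to 1.25 (protocol 13.6.2). True ratio 1 and 45 per arm (SAP section 3).

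**Formulas.**
- Log-scale SD: σ = √ln(1 + CV²) = √ln(1.1225) = 0.340.
- Standard error of the difference between two arms: SE = σ√(2/n).
- Limits: ln 0.80 = −0.2231 and ln 1.25 = +0.2231. True difference: ln 0.95 = −0.0513, or ln 1 = 0.
- Normal approximation: power = Φ((0.2231 − δ)/SE − 1.645) + Φ((δ + 0.2231)/SE − 1.645) − 1, where δ is the true log difference.
- Exact: the same acceptance region with the t quantile on 2n − 2 degrees of freedom, integrated over the chi-square distribution of the variance estimate.

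**SAP figure (ratio 1, n = 45).** SE = 0.340 × √(2/45) = 0.0717. Each side: 0.2231/0.0717 − 1.645 = 1.47, so Φ = 0.929. Power ≈ 2 × 0.929 − 1 = 85.8%; exact 85.2%. The SAP's 85% reproduces.

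**Protocol figure (ratio 0.95, n = 47).** SE = 0.340 × √(2/47) = 0.0701. Lower side: (0.2231 − 0.0513)/0.0701 − 1.645 = 0.81, so Φ = 0.790. Upper side: (0.2231 + 0.0513)/0.0701 − 1.645 = 2.27, so Φ = 0.988. Power ≈ 0.790 + 0.988 − 1 = 77.8%; exact 77.2%. The protocol's 85% does not reproduce.

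**Exact power, one comparison and one parameter, CV 0.35:**

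| Per arm | Ratio 0.95 | Ratio 1.00 |
|---|---|---|
| 44 | 74.3% | 84.1% |
| 45 | 75.3% | 85.2% |
| 47 | 77.2% | 87.0% |

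With the SAP's 45 per arm but the protocol's ratio, power is 75.3%. The change of ratio, not of sample size, is what produces 85%.

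**Other readings of the protocol's inputs (47 and 44 per arm, ratio 0.95):**
- variance pooled over three arms (3n − 3 degrees of freedom): 77.4% and 74.5%;
- 0.35 taken directly as the log-scale SD: 74.7% and 71.6%;
- lower one-sided test only: 79.0% and 76.6%;
- untransformed and ratio-of-means (Fieller-type) versions: 60% to 71%.

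None comes near 85% at the stated alpha.

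**What 85% would require.**
- At ratio 0.95 and CV 0.35: 58 per arm (174 in total).
- At ratio 0.95 with 47 per arm: a CV of at most about 0.314 (0.303 with 44).
- At CV 0.35 with 47 per arm: a true ratio of about 0.977.

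**Dropout.** Going from 141 to 132 is a loss of 9/141 = 6.4%, not 5%. In the SAP, 45/0.95 = 47.4, which rounds up to 48 per arm rather than 47. Both gaps are small beside the power discrepancy.

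**Joint power.** By simulation for one parameter, with MB05 at 0.95 of two equal references, the chance of passing both MB05 comparisons is about 65% (47 per arm) or 60% (44). For all three comparisons it is about 60% or 55%.

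**The case against.** The arithmetic is not in dispute; the case on the other side concerns scope and weight.

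- **Scope.** Protocol 13.1 applies its planning ratio only to MB05 against each reference. If MB05 is at 0.95 of both, EU- against US-Synagis has a ratio of 1 and a power of 87.0% (47 per arm) or 84.1% (44). This stands: the 77% and 74% belong to the MB05 comparisons.
- **Worst case.** A CV of 0.35 is the top of the reported range. At CV 0.30 and ratio 0.95, power is 87.7% with 47 per arm and 85.6% with 44; at CV 0.25 it is about 95%. This also stands, and the higher failure risk should be labelled as a worst-case figure. But the protocol states its 85% at 0.35, where it is wrong.
- **The SAP is later and its sum is right.** The SAP is dated June 2023, a year after the protocol, and the protocol leaves detailed methods to it. The protocol's 44 per arm would give 84.1% at a ratio of 1, so the 0.95 may be one superseded or mistaken input. That is plausible but not shown, and the SAP does not declare the change.
- **Wider Cmax limits.** SAP section 15.7 says 70.00% to 143.00% might be considered for Cmax, which would give over 99% power. That range is optional, is not the basis of the protocol's calculation, and does not cover AUC0-inf.
- **No effect on inference.** Low power raises the sponsor's risk of failing to show equivalence; it does not raise the rate of false equivalence claims. This is true, and it is why the remedy is confined to wording.

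**Conclusion.** The concern holds. At the protocol's own inputs, power for each MB05-versus-reference comparison on each parameter is about 77% with 47 per arm and 74% with 44 evaluable. That is 8 to 11 percentage points below the stated 85%. The corresponding risk of failing one such comparison is about 23% to 26% instead of 15%.

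These figures assume log-normal data, CV 0.35, a true ratio of 0.95 and limits of 80.00% to 125.00%. They are per comparison, not joint. The SAP's 85% is correct for its own inputs, but those inputs differ from the protocol's and the difference is not declared where the SAP says it will be.

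**What to change.** Use one set of planning assumptions in both documents, in one of two ways:

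- **Keep the ratio of 0.95.** Restate protocol 13.1 to say that, at CV 0.35 and a true ratio of 0.95, 47 per arm gives about 77% power (about 74% with 44 evaluable) for each comparison of MB05 with a reference product on each parameter. Bring SAP section 3 into line.
- **Adopt the SAP's assumptions.** State a ratio of 1, 45 evaluable per arm and 85% power in both documents, and give the power at 0.95 beside it (75.3% with 45 per arm, 77.2% with 47).

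Either way, say that the CV is the worst case, make clear which sample size is evaluable and which is enrolled, and record the difference from the protocol in SAP section 18. The cost is wording in two documents and a less favourable power figure. Enrolment and design stay as they are.

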# 13.2 Interim Analysis

A blinded interim analysis may be performed when 50% of the PK profiles are available in correlation with safety data to evaluate potential drug-related events. In this instance, blinded PK data would serve as preliminary assessment of the achievement of the therapeutic threshold for palivizumab (40  $\mu$ g/ml) This analysis of the PK in healthy adult volunteers, together with analytical comparability, may preliminarily inform about clinical extrapolation to the paediatric population.

# **13.3 Analysis Populations**

Population	Description
Safety	The safety population will include all randomised participants who received any amount of study treatment and will be summarised according to the treatment actually received, if this differs from that to which the participant was randomised to. The safety population will be used for the summaries of all safety, baseline and demographic data.
Pharmacokinetic	
 
The PK population will include all randomised participants where there is sufficient data for reliable estimates of Cmax (as determined by the study Pharmacokineticist).
 
Participants with dosing or PK sampling deviations that could potentially affect the PK profile will also be excluded from the PK population, at the discretion of the study Pharmacokineticist.
 
The PK population will be used for the summaries of all PK data.
 

Immunogenicity	The immunogenicity population will include all randomised participants who receive any amount of study treatment and who have at least 1 evaluable immunogenicity parameter post-dose and

For the purpose of analysis, the following populations are defined for this protocol. The final definition of each population will be presented in the SAP.

Population	Description
	will be summarised according to the treatment actually received, if this differs from that to which the participant was randomised.
	The immunogenicity population will be used for the summaries of all immunogenicity data.

#### 13.4 Demographic and Baseline Data

Demographic data (eg. gender, age, race, ethnicity, and BMI) will be summarized for all participants in the Safety population using descriptive statistics (mean, standard deviation [SD], median, minimum, and maximum) and presented by treatment. Medical history will be listed for the Safety population.

Screening serology results (HIV-1, HIV-2, HBsAg, HBcAb, HCV) and COVID-19 (PCR or antigen) results will be listed only.

Concomitant medications taken after the start of study treatment will be summarised for the Safety population. Prior and concomitant medications will be coded using the latest version of the WHO Drug Dictionary, and summarised by drug class, generic name and treatment group. The recorded start/stop dates will be used to identify when a concomitant medication was taken during the study. Prior medications will be listed only.

## 13.5 Safety/Tolerability Data

All participants in the Safety population will be included in the safety and tolerability analysis. Baseline for analysis of physical examination, vital signs, and clinical laboratory data will be defined as the last evaluation done before administration of study drug for each participant.

Safety evaluations will be based on the incidence, severity and relationship of AEs and changes from baseline in body weight, physical examination findings, vital signs, clinical laboratory, and ECG results and injection site reactions.

Abnormalities in clinical laboratory parameters, and vital signs, will be based on predefined normal ranges and will be tabulated by treatment showing participant counts and percentages.

## 13.5.1 Adverse Event Data

The verbatim terms used in the eCRF by investigators to identify AEs will be coded using the current version of the Medical Dictionary for Regulatory Activities (MedDRA) by system organ class (SOC) and preferred term, classified from verbatim terms. The number and percentage of participants with treatment-emergent AEs (TEAEs) and serious TEAEs as well as the number of TEAEs and serious TEAEs will be summarized by SOC and preferred term and tabulated for each treatment. Summaries by severity and relationship will also be presented. The percentage of participants who discontinued treatment due to a TEAE will be summarized and tabulated for each treatment. The duration of AEs will be determined and included in the listings only.

# 13.5.2 Clinical Laboratory Data

Clinical laboratory data will be summarized by the laboratory parameter. Normal reference ranges and abnormal results will be used in the summary of laboratory data. Individual abnormal results will be flagged as being "Low" or "High." Observed values and changes from baseline for continuous clinical laboratory parameters will be summarized at each scheduled timepoint using descriptive statistics (n, mean, SD, median, minimum, and maximum) and tabulated for each treatment. Categorical clinical laboratory data will be summarized at each scheduled timepoint using participant counts and percentages and tabulated by treatment. This includes the number and percentage of participants with any CS laboratory abnormalities. A listing of participants with any laboratory results outside the reference ranges and deemed CS will be provided.

